4.11.12 Electrocardiograms

For quantitative ECG measurements (heart rate, PR interval, ORS duration, OT interval, and corrected QT intervals using Bazett and Fridericia correction methods), values during the double-blind period will be presented by treatment group for all visits.

The Bazett corrected QT (QTcB) will be calculated as

QTcB=QT/RR $^{0.5}$, where RR = 60/HR.

The Fridericia corrected OT (OTcF) will be calculated as

QTcF=QT/RR $^{0.33}$, where RR = 60/HR.

TP-GDO-WW-016-01 Confidential Version 7.0 Effective Date: 28Aug13 Version Date: 28NOV2018 Related to: SOP-GDO-WW-019

The following summaries and listings will be provided for the SAF and all SA237:

- A summary of 12-lead by treatment group at each specified visit.
- The number and percentage of subjects with a QTc (using Bazett and Fridericia corrected) of ≤450ms, >450 to ≤480ms, >480 to ≤500ms, and >500ms will be summarized by treatment group at each specified visit.
- The number and percentage of subjects with a QTc (using Bazett and Fridericia corrected) of an increase from baseline of >0 to ≤30ms, >30 to ≤60ms, and >60ms will be summarized by treatment group at each specified visit.
- The number and percentage of subjects with PR interval values ≤120ms, >120 to ≤220ms, and >220ms, and the number and percentage of subjects with QRS interval values ≤60ms, >60 to ≤120ms, and >120ms will be presented by treatment group at each specified visit.
- A summary of incidence of treatment-emergent abnormality 12-lead ECG findings after start of study drug by treatment group.
- A by-subject listing of abnormal 12-lead ECG data will be provided.

4.11.13 Vital Signs, Physical Findings and Other Observations Related to Safety

Noninvasive pulse rate, temperature, systolic blood pressure (SBP) and diastolic blood pressure (DBP) will be measured at visits with the subject in a sitting position after at least 10 minutes at rest, according to the tabular schedule of study procedures in the protocol. Summary statistics of the actual measurement and their changes from baseline will be presented by treatment group at each specified visit.

In addition, summary statistics for the actual value and change from baseline will be presented by treatment group for all visits during the double-blind period.

Abnormal vital sign criteria as follows:

- diastolic blood pressure [DBP]: <50, >100 mmHg
- systolic blood pressure [SBP]: <90, >160 mmHg
- pulse rate [PR]: <60, >100 bpm
- Temperature: <36.0, >38.0

The following summaries and listings will be provided:

- A summary of pulse rates temperature, blood pressure and change from baseline by treatment group and visit.
- The number and percentage of subjects with abnormal vital signs during double-blind period by treatment group.
- A by-subject listing of vital signs.

4.12 Pharmacokinetics and Pharmacodynamics

TP-GDO-WW-016-01 Confidential Version 7.0 Effective Date: 28Aug13 Version Date: 28NOV2018

Related to: SOP-GDO-WW-019

Version Date: 28NOV2018

Page 33 of 60

The serum SA237 concentrations will be reported using the PK-PPS. The PD variables (IL-6, sIL-6R, hsCRP, anti-AQP4Ab, Plasmablast) will be reported using the SAF population.

To determine concentrations of SA237, serum samples will be drawn at various time points throughout the study. At Week 0, blood specimens for PK and PD samples will be collected prior to first dose administration of study drug (blank value). At other visits, PK and PD samples will be collected along with hematology samples at any time prior to drug administration according to the Schedule of Study assessments.

To support the Japanese BLA, the following reports will be produced. SA237 concentrations and PD variables in serum will be listed and summarized using descriptive statistics (including geometric mean and CV%, arithmetic mean and SD, median, observed maximums and minimums, and sample size). Arithmetic mean ± SD serum concentration-time profile and combined all subjects' serum concentration-time profiles (spaghetti plot) will be plotted using linear and semi-log scale. In addition, individual serum concentration-time profile will be plotted for each subjects using linear and semi-log scale. Summary tables and figures of SA237 concentration and PD variables will be provided as follows:

Concentration of SA237 and PD variables (absolute values as well as change from baseline) in serum will be summarized using descriptive statistics and arithmetic mean \pm SD serum concentration-time profile will be plotted by following subgroup using linear scale.

Samples that were excluded from the summary statistics will be marked in the listing.

The rule for summary of titer for anti AQP4 antibody status is defined in appendix 7.6.

Summary tables, figures, and listings of SA237 concentration and PD variables will be provided as follows:

- Summaries of concentrations of SA237 by visit will be presented by age category, Japanese/non-Japanese, relapse/no-relapse, ADA status, and overall.
- Summary of concentration of IL-6, sIL-6R, and hsCRP by visit will be presented by age category, Japanese/non-Japanese, relapse/no-relapse and overall in each of treatment group.
- Summary of titer for anti AQP4 antibody status, Plasmablast (Plasmablasts/CD19+ (%), Plasmablasts/CD45+ (%), and Plasmablasts (cells/uL)), and CD19+ cells (CD19+/CD45+ (%) and CD19+ (cells/uL)) by visit will be presented by NMO/NMOSD and AQP4 Status, relapse/no-relapse and overall in each of treatment group.
 - *Plasmablast and CD19+ cells will be calculated by following equation
 - O Plasmablasts (cells/uL) = CD45+Abs * Plasmablasts/CD45+ (%)

Confidential

- \circ CD19+ (cells/uL) = CD45+Abs * CD19+/CD45+ (%)
- A by-subject listing of concentration of SA237 in serum.
- A by-subject listing of IL-6, sIL-6R, and hsCRP

TP-GDO-WW-016-01 Effective Date: 28Aug13 Related to: SOP-GDO-WW-019 Version 7.0 Version Date: 28NOV2018

- A by-subject listing of anti-AQP4 antibody (positive/negative and titer)
- Plasmablast (Plasmablasts/CD19+(%), Plasmablasts/CD45+(%), and Plasmablast (cells/uL)), and CD19+ cells (CD19+/CD45+(%) and CD 19+ (cells/uL))
- A by-subject spaghetti plot of concentration for SA237 in serum by subgroup (age category, Japanese/non-Japanese, relapse/no-relapse, ADA status) using linear scale and overall using linear and semi log scale.
- A by-subject spaghetti plot of the absolute value and the change from baseline for concentration of IL-6, sIL-6R, and hsCRP by treatment group using linear and semi log scale.
- A by-subject spaghetti plot of the absolute value for concentration of IL-6, sIL-6R, and hsCRP by subgroup (age category, Japanese/non-Japanese, relapse/no-relapse, ADA status) in each of treatment group using linear scale
- A by-subject spaghetti plot of the absolute value for concentration of IL-6, sIL-6R, and hsCRP by treatment group in each subgroup (relapse/no-relapse, ADA status) using linear scale
- A by-subject spaghetti plot of the absolute value and the change from baseline for titer of anti-AQP4 antibody, Plasmablast (Plasmablasts/CD19+ (%), Plasmablasts/CD45+ (%), and Plasmablasts (cells/uL)), and CD19+ cells (CD19+/CD45+ (%), and CD19+ (cells/uL)) by treatment group using linear and semi-log scale
- A by-subject spaghetti plot of the absolute value for titer of anti-AQP4 antibody, Plasmablasts (Plasmablasts/CD19+ (%), Plasmablasts/CD45+ (%), and Plasmablasts (cells/uL)), and CD19+ cells (CD19+/CD45+ (%), and CD19+ (cells/uL)) by subgroup (NMO/NMOSD and AQP4 Status, relapse/no-relapse) in each of treatment group using linear scale.
- A by-subject spaghetti plot of the absolute value for titer of anti-AQP4 antibody, Plasmablast (Plasmablasts/CD19+ (%), Plasmablasts/CD45+ (%), and Plasmablasts (cells/uL)), and CD19+ cells (CD19+/CD45+ (%), and CD19+ (cells/uL)) by treatment group in each subgroup (NMO/NMOSD and AQP4 Status, relapse/no-relapse) using linear scale.
- An Arithmetic mean \pm SD plot of concentration for SA237 in serum by subgroup (age category, Japanese/non-Japanese, relapse/no-relapse, ADA status) using linear scale and overall using linear and semi log scale.
- An Arithmetic mean ± SD plot of the absolute value and the change from baseline for concentration of IL-6, sIL-6R, and hsCRP by treatment group using linear and semilog scale.

TP-GDO-WW-016-01 Confidential Version 7.0 Effective Date: 28Aug13 Version Date: 28NOV2018

Page 36 of 60

- An Arithmetic mean ± SD plot of the absolute value for concentration of IL-6, sIL-6R, and hsCRP by subgroup (age category, Japanese/non-Japanese, relapse/no-relapse, ADA status) in each of treatment group using linear scale.
- An Arithmetic mean ± SD plot of the absolute value for concentration of IL-6, sIL-6R, and hsCRP by treatment group in each subgroup (age category, Japanese/non-Japanese, relapse/no-relapse, ADA status) using linear scale
- An Arithmetic mean ± SD plot of the absolute value for titer of anti-AQP4 antibody, Plasmablast (Plasmablasts/CD19+ (%), Plasmablasts/CD45+ (%), Plasmablasts (cells/uL)), and CD19+ cells (CD19+/CD45+ (%) and CD19+ (cells/uL)) by treatment group using linear and semi-log scale
- An Arithmetic mean ± SD plot of the absolute value for titer of anti-AQP4 antibody, Plasmablasts (Plasmablasts/CD19+ (%), Plasmablasts/CD45+ (%), Plasmablasts (cells/uL)), and CD19+ cells (CD19+/CD45+ (%) and CD19+ (cells/uL)) by subgroup (NMO/NMOSD and AQP4 Status, relapse/no-relapse) in each of treatment group using linear scale
- An Arithmetic mean ± SD plot of the absolute value for titer of anti-AQP4 antibody, Plasmablast (Plasmablasts/CD19+ (%), Plasmablasts/CD45+ (%), Plasmablasts (cells/uL)), and CD19+ cells (CD19+/CD45+ (%) and CD19+ (cells/uL)) by treatment group in each subgroup (NMO/NMOSD and AQP4 Status, relapse/no-relapse) using linear scale.
- A by-subject listing of actual doses, date and time of sampling, visit, relative day, and the accession number.
- Scatter plot of anti-AQP4 antibody titer versus plasmablast (Plasmablasts/CD19+ Plasmablasts/CD45+ (%), Plasmablasts (cells/uL)) will be presented at Weeks 0, 2 and 4, 8, 12, 24, and Q24W. When the data of anti-AQP4 antibody is negative, put "1" as a titer for negative samples and replace to "BLQ".
- Scatter plots of serum SA237 concentration versus body weight at weeks 2, 4, Q4W respectively.

4.13 Immunogenicity

ADA subgroup using confirmatory sample status are defined as below.

- ADA negative subjects: subjects without positive ADA during study. If sample at baseline is missing and no sample after the baseline is positive, the subject is defined as" ADA negative subjects".
- ADA unaffected subjects: subjects who have pre-existing ADA (POSITIVE at baseline) that was NOT boosted to a higher level after the post dose. "NOT boosted

TP-GDO-WW-016-01 Confidential Version 7.0 Effective Date: 28Aug13 Version Date: 28NOV2018

- to a higher level" means that ADA titer after the baseline is <fourfold than the ADA titer at baseline.
- Treatment-boosted ADA subjects: subjects who have pre-existing ADA that was boosted to a higher level at least one time point after baseline "Boosted to a higher level" means as follow
 - 1) ADA titer after the baseline is greater fourfold than the ADA titer at baseline
- Treatment-induced ADA subjects: subjects who have positive ADA not at baseline but after the baseline. If sample at baseline is missing and at least one sample after the baseline is positive, the subject is defined as" Treatment-induced ADA subjects"

The immunogenicity will be analyzed using the SAF population.

- The numbers and proportions of subjects with positive ADA at baseline will be presented by treatment group and overall.
- The numbers and proportions of ADA negative subjects, ADA unaffected subjects, treatment-boosted ADA subjects, and treatment-induced ADA subjects will be summarized. The numbers and proportions of transient ADA and persistent ADA will be summarized in the treatment-induced ADA subjects.

Transient ADA: 1) Treatment-induced ADA detected only at one sampling time point (excluding the last sampling time point) during the study or 2) treatment-induced ADA detected at two or more sampling time points during the study, where the period between first and last ADA-positive sampling time points is less than 16 weeks, and the subject's last sampling time point is ADA-negative.

Persistent ADA: 1) Treatment-induced ADA detected at two or more sampling time points during the study, where the period between first and last ADA-positive sampling time points is 16 weeks or longer or 2) where the period between first and last ADA-positive sampling time points is less than 16 weeks, and the subject's last sampling time point is ADA-positive or 3) treatment-induced ADA detected only at the last sampling time point.

- > The numbers and proportions of patients with positive/negative anti-SA237 antibodies and neutralizing antibodies will be presented at Week 0 and Q4W in SA237 group by visit.
 - A by-subject listing of anti-SA237 antibody (confirmatory judgment (positive/negative), titer, ratio of peak titer/baseline titer, and ADA subgroup), neutralizing judgment (positive/negative)), and adverse events in the subject having anti-SA237 antibody at least once at any point in time.

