- Hepatitis B viral DNA must be monitored in patients for whom a positive result for HBsAb is not clearly associated with vaccination against hepatitis B virus and HBV DNA is negative at screening or whom HBcAb is positive and HBV DNA is negative at screening.
- Perform C-SSRS

Safety

- AEs and concomitant medications will be monitored and recorded throughout the study.

Efficacy

- Relapse assessment will be monitored and recorded throughout the study.

Every 24 Weeks

- Administer satralizumab injection (SC) after all other study-related procedures have been performed.
- Record body weight.
- Perform physical exam.
- Record vital signs.
- ECG should be performed prior to blood draws.
- Perform pregnancy test for females of child-bearing potential. Serum or urine [sensitivity of at least 25 mIU/mL] β -hCG will be performed.
- Laboratory test: RBC, Hb, HCT, WBC, WBC differentiation, PLT, INR, fibrinogen, total protein, albumin, total bilirubin, ALP, AST, ALT, γ -GTP, LDH, total cholesterol, LDL, HDL, triglyceride, ferritin, BUN, creatinine, CK, Na, Cl, K, Ca, P, complement (CH50, C3, C4), uric acid, urinary glucose, urinary protein, urinary occult blood, urobilinogen.
- Hepatitis B viral DNA must be monitored in patients for whom a positive result for HBsAb is not clearly associated with vaccination against hepatitis B virus and HBV DNA is negative at screening or whom HBcAb is positive and HBV DNA is negative at screening.
- Perform C-SSRS

Safety

- AE and concomitant medications will be monitored and recorded throughout the study.

Efficacy

- Relapse assessment will be monitored and recorded throughout the study.
- Perform EDSS/FSS.
- Visual Function Testing (visual function testing includes visual acuity tests of Snellen and Low-contrast Sloan letter chart. Visual acuity test of Snellen chart is not required if it is implemented with FSS assessment), SF-36, VAS for pain, FACIT-fatigue, mRS, EQ-5D and T25W.
- ZBI which is optional and will be performed (window in days is within ± 28 days) for caregiver who signed informed consent to caregiver burden assessment.

PK-PD

- Obtain PK sample

Immunogenicity

- Collect sample for anti-drug antibody

During the Extension Period, when extra visits at relapsing occur, the following procedures will be performed:

- Perform physical exam
- Record Vital signs

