4.10.1.5 Examination of Subgroups

The primary and key secondary endpoints (TFR, change from baseline to week 24 in pain and fatigue) will be summarized by the following subgroups:

- NMO/NMOSD and AQP4 Status at screening (5 categories: NMO, NMOSD, NMO and AQP4 positive, NMO and AQP4 negative, and NMO/NMOSD and AQP4 positive)
- Geographical region (Asia, Others).
- Prior therapy for prevention of NMO/NMOSD attack (B-cell depleting therapy or immunosuppressants/others)
- Most recent attack in the last one year prior to screening (first attack or relapse).
- ADA status (ADA negative subjects, ADA unaffected subjects, Treatment-boosted ADA subjects, Treatment-induced ADA subjects) (see Section 4.13)

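### SAP 4.13 leaves a baseline-ADA-positive patient with a peak titre of exactly four times baseline in no ADA class

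*SAP*

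**What the plan says.** SAP 4.13 defines four ADA classes: negative, unaffected, treatment-boosted and treatment-induced. Two of them apply to patients who are already positive at baseline:

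- **Unaffected** is introduced as pre-existing ADA that was not boosted. That is then given a numerical meaning: "ADA titer after the baseline is <fourfold than the ADA titer at baseline".
- **Treatment-boosted** is pre-existing ADA raised at one or more time points after baseline, where raised means "ADA titer after the baseline is greater fourfold than the ADA titer at baseline".

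SAP 4.10.1.5 makes these classes a subgroup factor for time to first relapse, pain and fatigue: "ADA status (ADA negative subjects, ADA unaffected subjects, Treatment-boosted ADA subjects, Treatment-induced ADA subjects". SAP 4.11.1 carries the same subgroups into the main safety summaries. SAP 4.12 uses ADA status for the satralizumab concentration summaries and for plots of concentration and of IL-6, sIL-6R and hsCRP. The by-subject listing in SAP 4.13 prints both the ratio of peak to baseline titre and the ADA subgroup.

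**The concern.** The two numerical conditions are strict inequalities on either side of the same value, so the value itself belongs to neither class. Titres from a serial dilution take only a few discrete ratios, and 4 can be one of them. A patient at that value could be coded as unaffected (because not boosted), as boosted (reading the phrase loosely as fourfold or greater), or as unclassified (reading it literally). Two programmers working independently could produce different tables from the same data, and on the literal reading the four classes would not add up to the safety population.

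**Working it through.** The plan gives no figure to reproduce; the check applies the rules as written.

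**Input.** Let R be the highest post-baseline ADA titre divided by the baseline titre, for a patient positive at baseline. From SAP 4.13, unaffected means R < 4 and boosted means R > 4 (literal reading).

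| R | As written | If boosted is R ≥ 4 |
|---|---|---|
| 1 | unaffected | unaffected |
| 2 | unaffected | unaffected |
| 3.9 | unaffected | unaffected |
| 4 | no class | boosted |
| 4.1 | boosted | boosted |
| 8 | boosted | boosted |
| 16 | boosted | boosted |

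The other two classes do not catch the patient. ADA negative needs no positive sample, and treatment-induced needs a baseline that is not positive.

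**Can R equal exactly 4?** The documents do not state the ADA dilution factor, so this is shown over a range of assumptions:

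- twofold series: ratios 1, 2, 4, 8, so yes, after two steps (2 × 2 = 4);
- fourfold series: ratios 1, 4, 16, so yes, after one step, the smallest possible rise;
- threefold series: ratios 1, 3, 9, so no;
- tenfold series: ratios 1, 10, 100, so no.

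The titre rule in SAP 7.6 concerns the anti-AQP4 assay and does not settle this.

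**Do the transient and persistent rules in the same section have a similar gap?** They do not. For a treatment-induced patient, take the number of positive samples, the span from first to last positive, and the status of the last sample:

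- one positive, not the last sample: transient ("Treatment-induced ADA detected only at one sampling time point (excluding the last sampling time point) during the study");
- one positive, the last sample: persistent;
- two or more positives, span of 16 weeks or more: persistent ("the period between first and last ADA-positive sampling time points is 16 weeks or longer");
- two or more positives, shorter span, last sample negative: transient ("less than 16 weeks, and the subject's last sampling time point is ADA-negative");
- two or more positives, shorter span, last sample positive: persistent.

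These five cases cover everything and do not overlap. Enumeration agrees. Seven 24-weekly samples give 2^7 − 1 = 127 possible patterns with at least one positive: 6 transient, 121 persistent, none unclassified. Twelve samples to Week 48, 4-weekly, give 2^12 − 1 = 4,095 patterns, none unclassified. Those twelve followed by three 24-weekly samples give 2^15 − 1 = 32,767 patterns, none unclassified.

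**The case against.** The best defence is that this is a slip of wording. The phrase for boosted lacks a word and may well mean fourfold or greater, and unaffected is introduced as not boosted, so the classes were intended as complements. The listing of peak-to-baseline ratio beside ADA subgroup would also make an affected patient visible. All of this is fair, and it limits the importance of the point. It does not remove it: the intended reading is not the one written, the two available clues place a ratio of 4 in different classes, and a SAP should be programmable without choosing between them.

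A reader might go further and infer that the 16-week rule for transient and persistent ADA breaks down after extension Week 48, because Protocol Table 8 then schedules ADA sampling only every 24 weeks. The documents do not support that:

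- The rules give every pattern exactly one class on any schedule, as shown above.
- With windows of ±7 days, two successive scheduled positives are at least 24 − 2 = 22 weeks apart. Calling them persistent is correct by the SAP's own 16-week criterion.
- Patients who pass extension Week 48 already have scheduled 4-weekly samples from the double-blind period and from the extension up to that point. Counting them does not count doubtful labels.
- The 71% ADA rate in Protocol 5.1.1.6 comes from the double-blind period, where sampling is 4-weekly throughout. It says nothing about late-extension antibodies.

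What remains is modest. An isolated positive after extension Week 48 lies between scheduled negatives that are 48 weeks apart nominally, or 46 to 50 with the windows. Its transient label therefore says little about how long the antibody lasted.

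**Conclusion.** The gap at exactly fourfold is real as written and should be closed. It is a minor wording defect: it can affect only patients who are ADA-positive at baseline and whose peak ratio is exactly 4. Their number is likely small but cannot be calculated, because neither the dilution series nor the baseline-positive count is given. If the series is threefold or tenfold, the value cannot arise at all. The consequence is confined to the ADA summary and to the subgroups and displays by ADA status; the primary comparison of time to first relapse in the full population does not change. The conclusion rests on reading the phrase for boosted as strictly more than fourfold. The transient and persistent rules can be derived as they stand and need no correction.

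**What to change.** In SAP 4.13, define treatment-boosted as a titre at least four times (≥ 4) the baseline titre at one or more post-baseline time points, and ADA unaffected as a titre below four times baseline at every post-baseline sample. Every baseline-positive patient with post-baseline titres then falls in exactly one of the two classes. The cost is a short text edit and the matching line of code, with no new samples or analyses.

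Leave the transient and persistent rules unchanged. In particular, do not stop that classification at extension Week 48. A patient positive only at that visit and negative at Week 72 is transient under the present rules, but would become persistent if the later negative were discarded, because the sole positive would then be the last sample. At most, add a note when reporting that an isolated positive after extension Week 48 carries little information on duration.
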